#### **4.4 Sample size calculation**

The primary outcome will be improvement of the Microvascular Health Index after 3 months. The sample size is chosen according to a pilot study with 13 healthy volunteers receiving the food supplement Endocalyx™ for 3 consecutive months. After 3 months, a 31% improvement in Microvascular Health Index was demonstrated, expressed in a significant increase of the MHI from 1.05 at baseline, to 1.38 at 3 months (improvement of 0.33).

Group sample sizes of 23 per group achieve 80% power to detect a difference of 0.35 between the null hypothesis that group improvement means are 0.0 and the alternative hypothesis that the improvement mean of group 2 or 3 is 0.35 with estimated group standard deviations of 0.41 with a significance level (alpha) of 0.05000 using a two-sided two-sample t-test. If we anticipate a 25% drop out rate per group, we will need 30 patients per group.

Therefore, we decided to enrol a total number of 90 patients in this study.

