#### 7.1.2 Secondary study parameters/endpoints

Secondary endpoints include;

- Albuminuria: urinary excretion of albumin, using albumin/creatinine ratio in mg/mmol.
- Inflammation: urinary heparanase and MCP-1 expression, serum C-reactive protein, and MCP-1 levels.
- Metabolic response: fasting glucose, HbA1c, C-peptide, IGF-1, total cholesterol, LDL cholesterol, HDL cholesterol, triglycerides levels, body weight, waist circumference, waist-to-hip ratio and systolic blood pressure.
- Identifying specific urinary heparan sulfate domains.

To evaluate the legacy effects of the interventions, the primary and secondary parameters will also be assed three months after stopping the intervention.

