### 9.2 Secondary study parameters

The categorical data will be summarized by the frequencies and percentages and tested within the group between baseline and 3 months using a Pearson's Chi-squared test. The continuous data will be summarized in mean with standard deviation in case of normal distribution or median with interquartile range in case of non-normal distribution. A paired two-tailed Student's t test or Wilcoxon signed rank test will be used to calculate the effect within the group between baseline and 3 months.

Differences in outcomes between the groups (diet vs placebo and supplement vs placebo) will be tested with a Student's t test for normally distributed data or Mann-Whitney *U* test for non-normally distributed data.

A paired two-tailed Student's t test or Wilcoxon signed rank test for differences of the primary and secondary parameters between baseline and 6 months within the group will be used to evaluate the legacy effect of the interventions 3 months after stopping with the intervention.

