### 9.3 Other study parameters

Demographic data and other baseline characteristics will be summarised using descriptive statistics. The main analyses will also be performed in a priori defined subgroup analyses such as age at baseline, smokers vs non-smokers ect.

Additional explorative analyses involve the analysis of prognostic and predictive factors for achieving the primary or secondary endpoint, this will be investigated by using logistic regression. The level of significance for all tests will be set at  $p<0.05$ .

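### Eighteen secondary endpoints are tested against placebo in two contrasts at p<0.05 with no hierarchy, error control or exploratory label, so a chance finding is likely; the legacy effect rests on within-arm tests

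*Combined protocol and SAP*

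**What the plan says.** Section 7.1.2 lists the secondary endpoints in four groups: albuminuria (albumin/creatinine ratio), four inflammation markers, a metabolic group that begins "Metabolic response: fasting glucose, HbA1c, C-peptide, IGF-1, total cholesterol, LDL cholesterol, HDL cholesterol, triglycerides levels" and adds four physical measures, and urinary heparan sulfate domains, whose number is not given.

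Section 9.2 states: "Differences in outcomes between the groups (diet vs placebo and supplement vs placebo) will be tested with" a t test or Mann-Whitney test. It also plans paired tests within each arm from baseline to 3 months. For the legacy effect, it names only paired within-arm tests from baseline to 6 months, covering the primary and secondary parameters.

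Section 9.3 closes with one rule: "The level of significance for all tests will be set at" p<0.05. The only analyses that section 9 calls explorative are those of prognostic and predictive factors. The sample size in section 4.4 concerns MHI alone: "Group sample sizes of 23 per group achieve 80% power to detect a difference of 0.35", "with a significance level (alpha) of 0.05000 using a two-sided two-sample t-test".

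**The concern.** The plan sets one threshold for all tests and does not say which secondary results would carry weight. The Summary and section 2 word the secondary aims as directional effects: lower inflammation, less albuminuria, better metabolic values. Two of these aims pool several markers, and there is no rule for how many must move or which ones. Followed literally, the plan would let an isolated p<0.05 on one marker be reported as support for the whole aim.

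Albuminuria shows the problem. The Summary, section 10.3 and section 12.1 make it central to the rationale, but section 9 never mentions it. It comes first in the list in section 7.1.2 and third of four in section 2, so list order gives it no rank. In the analysis it weighs as much as waist-to-hip ratio.

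The within-arm tests raise a second problem. A change from baseline in one arm can come from a time trend, regression to the mean or altered co-medication. Sections 5.2 and 5.3 allow antihypertensive and glucose-lowering drugs to be changed during the study. A legacy claim resting on such a test would have no control behind it.

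**Working it through.** **The plan's own figure.** Section 4.4 uses a difference of 0.35, "estimated group standard deviations of 0.41", two-sided alpha 0.05 and 23 per group. The noncentrality is 0.35 / (0.41 × √(2/23)) = 2.89 on 44 degrees of freedom, which gives power 80.8%. With 22 per group it is 79.0%. The stated 23 is reproduced. It concerns MHI only; the documents state no error rate for the secondary family.

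**Count of secondary endpoints (section 7.1.2).**
- Albuminuria: 1
- Inflammation: 4 (urinary heparanase, urinary MCP-1, serum CRP, serum MCP-1)
- Metabolic: 8 laboratory + 4 physical = 12
- Heparan sulfate domains: at least 1
- Total: 1 + 4 + 12 + 1 = 18

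**Between-arm tests at 3 months.** Section 9.2 gives two contrasts per endpoint: 18 × 2 = 36. Section 2 and the Summary supply the 3-month time point.

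**Expected false positives if neither intervention works.** 36 × 0.05 = 1.8, whatever the correlation. For one contrast: 18 × 0.05 = 0.9.

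**Chance of at least one, if tests are independent.**
- Both contrasts: 1 − 0.95^36 = 84%
- One contrast: 1 − 0.95^18 = 60%
- Inflammation markers only, one contrast: 1 − 0.95^4 = 19%
- Metabolic markers only, one contrast: 1 − 0.95^12 = 46%

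**Allowing for dependence.** Section 3 makes one placebo arm the control for both contrasts, and several endpoints are plainly related (total and LDL cholesterol, glucose and HbA1c, weight and waist). The documents give no correlations, so a common value ρ is assumed. The figures come from simulating 18 endpoints in three equal arms, with all null hypotheses true and two-sided tests at 0.05.

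| Assumed ρ | At least one of 36 |
|---|---|
| 0 | 82% |
| 0.1 | 81% |
| 0.2 | 78% |
| 0.3 | 73% |
| 0.5 | 61% |
| 0.7 | 45% |

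The expected number stayed at 1.8 in every row. The count leaves out any further heparan sulfate domains, the per-protocol results (section 7.2) and the subgroup analyses (section 9.3).

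**Within-arm tests.** These are left out of the count. Their null hypothesis is no change over time, which can be false when the intervention does nothing. Multiplying their number by 0.05 would therefore not count false treatment effects.

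**The case against.** The best defence is that the plan promises nothing about the secondary endpoints. MHI is clearly primary and the sample size rests on it alone. The Summary describes the secondary objective as monitoring dietary effects, and no section says that one nominal result settles a secondary aim. This stands in part: no stated error rate is broken. It does not close the gap, because section 9.3 sets its threshold for all tests, section 9 gives the exploratory label to other analyses only, and the aims are worded as effects.

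A second defence is that the two interventions are separate questions, so the family is 18 tests and not 36. That is a fair choice of family. It lowers the expectation to 0.9 and the ceiling to 60%, which still leaves the problem.

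A reader might infer that a chance finding is almost certain. The documents do not support that. The ceiling is 84% under independence, and the shared placebo arm and related endpoints pull it down. A reader might also add the within-arm tests to reach a much larger total, but those tests do not measure a difference from placebo.

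Finally, a reader might conclude that albuminuria must become a gated key endpoint. That is a trade-off, not a correction. Behind a gate on MHI, albuminuria could not be claimed about 20% of the time in each contrast even under the design assumptions (100% − 80% power), and the documents give no power for albuminuria itself.

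**Conclusion.** The concern holds at this strength. With 18 secondary endpoints in two placebo contrasts at p<0.05, about two false positives (1.8) are expected if neither intervention works, and at least one is likely. The chance is 84% as a ceiling under independence, and about 82% to 45% with a shared placebo arm and assumed correlations of 0 to 0.7. The range rests on that assumed common correlation, on all null hypotheses being true, and on counting the heparan sulfate domains as one endpoint. For a single contrast the ceiling is 60%.

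The within-arm tests are a separate weakness in the same section. As the only tests named for the legacy effect, they cannot support a claim that an intervention caused a lasting change.

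The primary MHI analysis is not affected by this point. What is missing is a label and a claim rule for the secondary results.

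**What to change.** In sections 9.2 and 9.3:

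1. Limit the p<0.05 claim rule to the two primary MHI contrasts with placebo.
2. State that all between-arm secondary results, including albumin/creatinine ratio, are reported as estimated differences with 95% confidence intervals and labelled exploratory.
3. State that within-arm p values at 3 and 6 months support no claim of an intervention effect or a legacy effect. This should cover MHI as well, since section 9.1 tests it within arms at 3 months and section 9.2 at 6 months.

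The cost is wording, settled before the data are seen. Sample size and primary power are unchanged. The downside is that isolated secondary p values below 0.05, including one for albuminuria, would no longer count as findings and would serve only to guide later work.

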## 10. ETHICAL CONSIDERATIONS

### 10.1 Regulation statement

This study will be conducted according to the principles of the Declaration of Helsinki (64th WMA General Assembly, Fortaleza, Brazil, October 2013) in accordance with the Medical Research Involving Human Subjects Act (WMO) and to the standards of Good Clinical Practice. The study protocol will be submitted for approval to the Medical Ethics Committee (METC) of the Leiden University Medical Center

### 10.2 Recruitment and consent

The study will not start before formal approval of the Medical Ethics Committee (METC) of the LUMC has been granted. Patients will be recruited at primary care centres in the The Hague region. The investigator or assigned research staff will provide oral and written information about the study and is responsible for the signed informed consent. Patients will be given as long as they require deciding if they want to participate in this study. Only after written informed consent is obtained will the patient be entered into the study.

### 10.3 Benefits and risks assessment, group relatedness

The prevalence of type 2 diabetes is high in South Asian patients [22]. These patients have a 40 times higher risk of developing ESRD and a faster progression to renal failure compared to West European patients [54]. This is may be linked to increased systemic and glomerular inflammation in these patients [24, 55, 56]. Consequently, these patients will probably have an impaired endothelial glycocalyx with high heparanase activity and would benefit the most from treatments that support the glycocalyx homeostasis and reduce inflammation burden. To date, treatments for diabetic nephropathy are insufficient in preventing the development of ESRD. The interventions in this study can be used as add-on dietary interventions to reduce residual albuminuria and progression of renal disease.

The intervention burden in the FMD arm is for 5 days a month and in the other arms by taking daily capsules. Blood and urine sampling and non-invasive SDF imaging will be done at 3 time points in all intervention groups. In addition, patients are frequently monitored due to the possible effects of the interventions on glucose levels and insulin sensitivity. For the FMD group this means frequently measuring glucose values trough a finger prick.

Patients in the diet group have a risk of the occurrence of hypoglycemia during the study. In the days of the diet, this risk is reduced by stopping the hypoglycemic drugs that can cause hypoglycemia. After the diet, patients are asked to measure their glucose levels regularly.

The dosages of the hypoglycemic drugs can be altered if needed.

Other risks of the interventions may be an allergic reaction to one of the components of the diet or the food supplement. However, if eligible patients already are known with specific food allergies, they are excluded from the study. Effects on kidney function and liver function will be monitored during the study, but are not expected as a result of the interventions. In our opinion, the risk of the interventions is reduced within our study design and therefore the limited side effects and possible beneficial effects of the interventions on metabolic parameters, microvascular health and albuminuria justify participation in this study.

#### **10.4 Compensation for injury**

The sponsor/investigator has a liability insurance which is in accordance with article 7 of the WMO. The sponsor also has an insurance which is in accordance with the legal requirements in the Netherlands (Article 7 WMO). This insurance provides cover for damage to research subjects through injury or death caused by the study.

The insurance applies to the damage that becomes apparent during the study or within 4 years after the end of the study.

#### **10.5 Incentives**

Participants will receive 200 euros to cover any expenses for participation in the study, which is composed of 40 euros per study visit. Patients that are withdrawn from the study will receive the incentive build up from baseline to the time point of the study visit they completed.

## 11. ADMINISTRATIVE ASPECTS, MONITORING AND PUBLICATION

### 11.1 Handling and storage of data and documents

The blood samples, urine as well as data and documents will be coded by a subject identification code. The identification code will consist of the protocol ID number "88"; followed by a consecutive number for the subject, for example; 88-01, 88-02. The blood and urine samples will be coded by this identification code without randomization number but followed by the number for the sampling. Examples: 88-01-T0 (meaning patient one, sampling at T0). 88-032-T4 (meaning patient thirty two, sampling at T4).

There will be a subject identification code list that links the codes to a subject. Only the principle investigators have access to the subject identification code list. The subject identification code list and the data will be stored separately for 15 years by the principal investigator.

The data collected during the study visits will be entered directly into the eCRF (Castor) with exception for the questionnaires, laboratory results and SDF imaging parameters. The questionnaires will be filled out by the patient on paper during the study visit. The SDF imaging parameters will be collected in the Glycocheck software system. Patients are entered into the Glycocheck software under the subject identification code. Only the sex of the patient will be added in the Glycocheck software. The laboratory results will be presented in HIX anonymously under patient name Glycotreat\_trail\_vrouw or Glycotreat\_trail\_man.. The investigator or research staff will enter this data into the eCRF. The questionnaire and laboratory source documents will be stored in a paper file in the LUMC. The Glycocheck software will be stored on a laptop in the LUMC.

Blood and urine samples will be sent to the Radboud UMC, these samples will be labelled with the subject identification code and sampling number. The identification key will be kept at the LUMC.

### 11.2 Monitoring and Quality Assurance

Monitoring will be done according to the monitor plan by internal monitors of the LUMC.

### 11.3 Amendments

A 'substantial amendment' is defined as an amendment to the terms of the METC application, or to the protocol or any other supporting documentation, that is likely to affect to a significant degree:

- the safety or physical or mental integrity of the subjects of the trial;
- the scientific value of the trial;

- the conduct or management of the trial; or
- the quality or safety of any intervention used in the trial.

All substantial amendments will be notified to the METC and to the competent authority. Non-substantial amendments will not be notified to the accredited METC and the competent authority, but will be recorded and filed by the sponsor.

#### **11.4 Annual progress report**

The sponsor/investigator will submit a summary of the progress of the trial to the accredited METC once a year. Information will be provided on the date of inclusion of the first subject, numbers of subjects included and numbers of subjects that have completed the trial, serious adverse events/ serious adverse reactions, other problems, and amendments.

#### **11.5 Temporary halt and (prematurely) end of study report**

The sponsor will notify the accredited METC and the competent authority of the end of the study within a period of 90 days. The end of the study is defined as the patient's last visit.

The sponsor will notify the METC immediately of a temporary halt of the study, including the reason of such an action.

In case the study is ended prematurely, the sponsor will notify the accredited METC and the competent authority within 15 days, including the reasons for the premature termination.

Within one year after the end of the study, the investigator/sponsor will submit a final study report with the results of the study, including any publications/abstracts of the study, to the accredited METC and the Competent Authority.

#### **11.6 Public disclosure and publication policy**

The study results will be published in medical journals.

## 12. STRUCTURED RISK ANALYSIS

### 12.1 Potential issues of concern

- a. Level of knowledge about mechanism of action.

#### Fasting mimicking diet

The fasting mimicking diet tricks the body into fasting which induces several beneficial effects by triggering (long lasting) adaptive cellular stress responses. The mechanisms that are typically induced by fasting due to metabolic shifts are a reduction of IGF-1 levels, insulin, fat storage, and endogenous glucose production, increased adipose lipolysis and fat oxidation, and use of glycerol and ketone bodies instead of glucose as preferred carbon sources. Moreover, it induces autophagy and reduces levels of pro-inflammatory cytokines and systemic inflammation [45].

#### Food supplement

The Endocalyx supplement combines three mechanisms to support the glycocalyx homeostasis; by supplying polysaccharides as glycocalyx constituents, stimulating glycocalyx synthesis by providing the substrate for glycosaminoglycan synthesis and by reducing reactive oxygen species-mediated endothelial dysfunction [57-59].

- b. Previous exposure of human beings with the test products and/or products with a similar biological mechanism.

#### Fasting mimicking diet

Two trials were conducted with healthy volunteers receiving the Prolon diet. The results are provided in paragraph 6.3.1.

#### Food supplement

A pilot trial was conducted among healthy volunteers with the food supplement. The results are provided in paragraph 6.3.2.

Several trials have been conducted with the individual ingredients of Endocalyx. Fucoidan extracted from brown marine algae has been studied individually or in a combined supplement in randomized placebo controlled trials [60-62] and in cancer patients [63, 64]. Brown algae seaweed supplements has also been studied in a small clinical trial with type 2 diabetic patients [65].

Hyaluronic acid and glucosamine sulfate are provided as supplements for patients with knee pain or osteoarthritis and have been studied in large randomized placebo controlled trials [66, 67]. Superoxide dismutase supplements have been studied in trials with middle-aged women and in adults with cardiovascular risk factors [68, 69]. Polyphenol supplements,

including grape polyphenols, have been studied in several human randomized controlled trials [70].

- c. Can the primary or secondary mechanism be induced in animals and/or in *ex-vivo* human cell material?

#### Fasting mimicking diet

The systemic effects of the fasting mimicking diet on inflammation, insulin, IGF-1 and glucose levels were also seen in experimental studies [37, 38, 71]. The results of experimental studies are explained in paragraph 6.2.1.

#### Food supplement

In the experimental study, the food supplement Endocalyx improved the microvascular health index, increased capillary density, lowered blood pressure and decreased mesenteric macrophage accumulation in old mice.

The individual ingredients of the food supplement have been studied in experimental studies and human cells.

Administration of fucoidan in diabetic rats improved the endothelial function shown as an upregulation of nitric oxide synthesis, improved blood pressure, and shear stress induced vasodilatation [72]. The anti-inflammatory, anticoagulant and anticoagulant effects of fucoidan extracted from 9 different brown seaweed species were investigated in rats and human umbilical vein endothelial cells [73].

Glucosamine hydrochloride induced the production of hyaluronan in human synovial cells and chondrocytes as it its incorporated and used for glycosaminoglycan synthesis [74].

Treatment with high molecular weight hyaluronan in diabetic mice reduced diabetes induced renal injury by modulating CD44 signaling, reduced NF- $\kappa$ B activation and the expression of inflammatory cytokines, but had no effect on blood glucose levels [75].

- d. Selectivity of the mechanism to target tissue in animals and/or human beings.

#### Fasting mimicking diet

The fasting mimicking diet has no specific target tissues, but obtains systemic effects triggered by cellular responses. Fasting mostly affects metabolic parameters and systemic inflammation.

#### Food supplement

The target site of the food supplement is the endothelial glycocalyx, which covers the endothelial cells of the systemic vasculature and therefore has systemic effects.

The ingredients of the Endocalyx went through a quality control for specification of composition and to detect contamination in the products (such as heavy metals or microbiology). These forms are provided in the supplementary.

Other toxicology studies and evaluation of the individual ingredients in animals or humans revealed no significant toxicological changes and confirmed the safety of the individual ingredients [67, 76, 77].

e. Analysis of potential effect.

Fasting mimicking diet

The Prolon diet is a pre-composed program that is provided in a box with separate boxes for each day. Therefore, the dosages of the ingredients remain the same throughout the study. In both clinical trials with the Prolon diet, no serious adverse effects were reported. The reported side effects were that of a low caloric diet such as mild fatigue, weakness, muscle aches, dry mouth and headache. The pilot study showed that changes in serum parameters for kidney and liver function remained within physiological ranges [38].

Food supplement

The pilot study with the Endocalyx food supplement reported no adverse effects of the supplement. One reported effect was dizziness, as endocalyx lowered the systolic blood pressure.

Studies with the individual ingredients:

Fucoidan: A study with rats to evaluate the anticoagulant effect of fucoidan extracted from *Laminaria japonica* showed no effects from daily administration of 300 mg/kg. Higher doses of 900mg/kg did however elevate clotting time [76].

In a study with volunteers taking 3 gram fucoidan per day, no clinical relevant changes was seen in coagulation markers [78]. In our study, patients receive about 400 mg fucoidan per day in the Endocalyx supplement, therefore, no effect on coagulation is expected.

Another randomized placebo-controlled trial with 300 mg fucoidan supplements showed no clinically significant change in blood safety markers (haematology or biochemistry) and that it was well tolerated without adverse effects [62]. Diarrhea was a reported side effect in patients taking 6 grams per day, which improved immediately after stopping fucoidan administration [79]. The last safety study with 20 healthy volunteers taking daily 4 gram fucoidan for two weeks showed no significant changes in haematological, kidney and liver parameters, and showed no significant changes in urine biochemical parameters or faecal and bowel states [80].

Hyaluronic acid: in several randomized controlled trials with oral administration of hyaluronic acid, with dosages ranging from 48 to 240 mg per day, no adverse events related to hyaluronan were reported [67]. A randomized controlled trial with patients taking daily 200 mg hyaluronan, no adverse changes in haematology, liver and kidney parameters were seen [81]. In our study, patients receive about 70 mg hyaluronic acid per day in the Endocalyx supplement.

Glucosamine sulfate: in large randomized placebo controlled trials with dosages of 1500 mg per day, no serious adverse effects linked to glucosamine sulfate occurred [66]. In our study, patients receive 1500 mg glucosamine sulfate per day in the endocalyx supplement.

Oxynea OMD-MVHS Blend SOD : there are no adverse effects reported in the studies with vegetable superoxide dismutase supplementation [82].

f. Pharmacokinetic considerations.

Fasting mimicking diet

Not applicable.

Food supplement

Fucoidan: limited research is available on the pharmacokinetic of fucoidan. Orally administered fucoidan was detected in small amounts the serum of healthy volunteers [83]. Others determined the concentration fucoidan in the liver after administration in rats, demonstrating systemic distribution [84].

Hyaluronic acid: in rats and dogs, orally administrated HA was degraded to oligosaccharides by intestinal bacteria, absorbed in the large intestine and is subsequently distributed throughout the tissues [85, 86].

Glucosamine sulfate is absorbed for 80% and is metabolized by the liver and excreted via urine. The half-life after oral administration is 60 hours [87].

Oxynea OMD-MVHS Blend SOD: a review on the bioavailability of polyphenols in humans showed that the mean time to reach maximum concentration of grape polyphenols (catechin) was 1.8 hours and for artichoke polyphenols (chologenic acid) 1.0 hours, with a half-live for catechin of 2.5 hours [88].

g. Study population.

For this study, south Asian patients, between 18 and 75 years, with diabetes mellitus type 2 and microalbuminuria will be included. If female and of child-bearing age, patient must be non-pregnant and non-breastfeeding.

h. Interaction with other products.

Fasting mimicking diet

Not applicable.

Food supplement

Several mouse studies indicated that intravenous glucosamine supplementation altered insulin sensitivity and glucose levels. However, randomized controlled trials with healthy individuals and type 2 diabetic patients demonstrated no significant increase in glycemic control, serum insulin or fasting glucose [89, 90]. During the study, glucose monitoring is done at the end of every month.

i. Predictability of effect.

Primary and secondary outcomes are the same for all the intervention arms.

Side dark field imaging is used to assess the effects of the interventions on the endothelial glycocalyx. A question can be whether mucosal glycocalyx thickness is representative for systemic changes. However, systemic activators in the diabetic environment will induce endothelial glycocalyx changes throughout the circulation. Changes in the mucosal glycocalyx were accompanied by changes in systemic glycocalyx thickness in diabetic patients [91]. In addition, glycocalyx changes in type 2 diabetic patients have shown to coincide in both the retinal and the sublingual microvasculature [92]. Heparan sulfate domains, heparanase, MCP-1 and albumin excretion are also used as parameters to evaluate the effect. Albuminuria is a known predictor of renal damage and a risk factor for renal failure. Furthermore, albuminuria is linked to dysregulation of the glycocalyx [1].

j. Can effects be managed?

Fasting mimicking diet

Patients receiving the fasting mimicking diet can return to their normal diet if there is a high incidence of adverse effect during the 5 days of the diet. Because of the low caloric intake during the diet, adequate measures are taken to prevent hypoglycemia induced by insulin or sulfonylureas. The dosages of these drugs are altered during the 5 days of the diet and patients are instructed to self-measure fasting glucose levels. At baseline, the instruction and

materials for self-measuring is provided to patients that use insulin or sulfonylurea derivatives. Moreover, a patient letter with the symptoms of hypoglycemia and instructions on what to do if the glucose level drops to 4.0 mmol/L, is provided to these patients. Patients that use long actin insulin during the diet are instructed to measure fasting glucose levels every day and track glucose levels during the second day of the diet. Patients that return to insulin or sulfonylurea derivatives are instructed to measure fasting glucose levels the 3 days after returning to their normal diet. These patients are contacted by the investigator or research staff by telephone. They are instructed to call the investigator if the glucose level drops to 4.0 mmol/L. At the end of the month, the last FMD cycle is evaluated for all patients together with additional glucose monitoring with a finger prick blood sample. If needed the dosages of hypoglycemic drugs can be altered. If the patients experience an allergic reaction to one of the ingredients of the Prolon diet, they are treated as mentioned in paragraph 5.4 and are withdrawn from the study. Effects on liver and kidney function are monitored during the study. The occurrence adverse effects is documented and evaluated at the end of every month.

